#### **Bi-Weekly Follow-Up Assessment**

**Overview:** Bi-weekly, participants will report on any occasion since the last assessment that the participant was out with the target friend in a social setting. For each such occasion, we will collect information about the context of these occasions (i.e., bar, party, out to dinner), whether there was alcohol, who was present, and whether there was an opportunity for intervention.

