**Stage 3 Procedures:**

*Intervention: FMI Mini-Controlled Trial with Intensive Follow-Up*

In this stage, we will test the finalized FMI (see **Screening, Eligibility, and Recruitment** above). To do this, we will contrast outcomes among those in this trial (N=24 dyads) with 24 pairs of friend dyads (total dyad N=48) who are randomly assigned to a wait list control condition.

The FMI will consist of a single session. Sessions will be offered on many days and times across the week to accommodate variability in student schedules. Each session will begin with a baseline assessment. In this session, women will be provided with the refined intervention protocol and will have the opportunity to role play and practice implementing the skills and strategies. Following the intervention, participants will be encouraged to utilize the skills and strategies presented in the intervention over the next 12 weeks, whenever they are out with their friend in a social context.

Dyad pairs assigned randomly (stratified on drinking levels, sexual assault history, and age) to the wait list control condition will be assessed once at baseline and again 12 weeks post-baseline. Assessment measures (baseline, 12 weeks) will mirror those administered to women in the FMI condition. At the completion of the 12 week “wait list,” participants will be administered the FMI and followed for 12 weeks. Comparison of outcomes across conditions will allow for stronger inferences about the efficacy of the intervention, will allow for examination of measurement reactivity, and will increase our sample size to examine within person change.

*Follow-up Assessments.* We will conduct bi-weekly online post-intervention assessments (with the first assessment to occur within 2 weeks of FMI completion) for 12 weeks. The bi-

weekly structure will optimally capture women's experiences applying strategies from the intervention. Participants will be reminded of follow-up assessments by phone, text, and email prompt. Individual members of the dyad will be interviewed in the unlikely event that the other member is lost to follow up over the brief follow-up period. At the end of the 12 weeks, participants will be contacted for an exit interview.

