*Stakeholder interviews.* In this second set of stakeholder interviews, we will gather information to inform next steps for the FMI intervention. To this end, a series of 5 interviews (2 randomly selected from prior interviews, 3 new to the project) will be conducted with campus administrators at Buffalo-area colleges. Selection will follow procedures outlined in Stage 1. In these interviews, the final FMI manual will be presented, and feedback would be solicited regarding ideas for scaling the FMI to other populations and contexts.

*Remuneration.* Students will receive electronic gift card payments of \$40 for the baseline assessment (which occurs just prior to the intervention) and \$20 for each post-intervention assessment. To encourage participant retention, participants who complete at least 4/6 bi-weekly assessments will receive a \$20 bonus. Stakeholders will receive \$25 in cash as a gesture of appreciation for participation.

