### **Instruments & Measures (For Stage 3)**

Data collection will occur at baseline and bi-weekly assessments, and a final evaluation that will be administered at the end of the last bi-weekly assessment. At baseline, we will collect demographic data, as well as drinking and sexual victimization history, and descriptive information regarding the relationship of the friends in our dyads. Other self-report measures will be administered both at baseline and then weekly during the follow-up periods (as denoted below). In the final (exit interview) evaluation, we will obtain feedback on participants' perceptions of the intervention and potential iatrogenic effects. All self-report measures may be completed prior to the session.

The proposed intervention will be designed to use relationship and responsibility in friend dyads as the basis for decreasing perceived barriers to intervention, improving readiness for helping friends, increasing knowledge about alcohol's effects on helping and strategies for overcoming or working around these effects, and imparting friend-based helping skills. These attitudes and behaviors will be the target intervention outcomes. Sexual assault will be examined as a secondary outcome. Changes in drinking also will be examined though this is not the principal focus of the intervention.

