A prominent feature of our design is that individuals are nested within dyads, and this necessitates a data analytic approach that can accommodate nested data structures. Hence, our Aim 3 analyses are built around hierarchical linear models (HLMs). First, we will evaluate group differences on variables from our first post-intervention assessment (i.e. perceived barriers, readiness, alcohol knowledge and strategies, and implementation of FAPBs) using a two level model (individuals nested within dyads). Treatment will be dummy coded (FMI vs. waitlist control group) and included as a level two covariate. Second, we will utilize all data from our three month follow-ups and repeat these analyses using a three-level model (6 repeated measures nested within individuals, and individuals nested within dyads). In these models treatment will be included as a level three covariate. We will use  $\beta$  to describe effect sizes (Cohen, 1988; Selya et al., 2012).

Our burst design provides a rich opportunity to examine whether changes in target constructs of interest (e.g., barriers, skills, alcohol knowledge and strategies) are associated with implementation of FAPBs. For these analyses we will combine the post-intervention data from our FMI and WLC groups after the latter has completed the intervention and follow-up assessments. Combining groups will increase our sample size and provide more stable estimates of effect sizes. For these analyses we will include reports of past week protective behavioral strategies just prior to the intervention and weekly aggregates of variables of interest from our three-month follow-up yielding 7 repeated measures nested within individuals and individuals nested within dyads. Time will be included as a level-1 covariate, and we will

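### The first bi-weekly survey's recall window is not anchored to the FMI session, so for women who complete baseline early, pre-FMI outings can be counted as post-intervention behaviour

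*Combined protocol and SAP*

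**What the plan says.** **Recall window.** Section 10.3, Bi-Weekly Follow-Up Assessment: "participants will report on any occasion since the last assessment that the participant was out with the target friend". The rule is the same for every survey, and nothing separate is said about the first.

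**Assessment points.** Section 10.3, Instruments & Measures (For Stage 3): "Data collection will occur at baseline and bi-weekly assessments, and a final evaluation".

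**Baseline timing, permissive.** The same paragraph adds: "All self-report measures may be completed prior to the session". It sets no limit on how long before. Section 25.2 describes the matching route for Studies 2 and 3, in which women consent online as they fill in the self-reports.

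**Baseline timing, restrictive.** Stage 3 Procedures: "Each session will begin with a baseline assessment". The Stage 3 remuneration text, repeated in Section 24.0, refers to the "baseline assessment (which occurs just prior to the intervention". The SAP's change analysis uses "reports of past week protective behavioral strategies just prior to the intervention". Section 9.1 places consent at the intervention session, after an overview of the study.

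**First follow-up.** Stage 3 Procedures schedules the bi-weekly surveys "with the first assessment to occur within 2 weeks of FMI completion".

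**Use in the analysis.** The SAP states that "we will evaluate group differences on variables from our first post-intervention assessment". It also computes a change effect size from baseline to the first follow-up, and treats that survey as one of seven waves in the pooled change models.

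**The concern.** A survey that is analysed as post-intervention should cover only time after the intervention. Here the window opens at whatever assessment came before, and for some women that could be a baseline completed online days before the session. No instruction to participants and no SAP rule removes outings that precede the FMI.

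Assault-prevention behaviour (FAPB) is a primary Aim 3 target and is reported by reference to outings. If untreated outings are mixed into the first survey, an immediate effect on a per-outing score is understated and the rise from the first to later waves is overstated. Section 16.2 says effect sizes are meant to inform later studies, so a distorted first-wave value would be carried forward.

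The wait-list arm has the same gap when it crosses over. Its last stated pre-FMI assessment is at 12 weeks, the FMI follows, and no maximum interval is given. This matters only for the pooled within-person analysis, because wait-list women are untreated in the between-group comparison.

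**Working it through.** **1. Is there a figure in the plan to reproduce?** No. The documents give no Stage 3 interval from baseline to session. The only sample-size statement (Section 16.2, 88 women, moderate to large effects) has no numerical inputs, and this point does not depend on it.

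**2. What has to be true for the problem to occur?** Two conditions must both hold:
- The woman completes baseline on an earlier day. Section 10.3 permits this; Stage 3 Procedures, the remuneration text and the SAP describe something else.
- The last assessment, at the first survey, means that baseline. The list of collection points in Section 10.3 supports this. Session-day forms described later in the same section could also qualify.

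If either fails, the untreated share is zero.

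**3. Share of the window when both hold.** Let g be the days from baseline to FMI and t the days from FMI to the first survey. With outings spread evenly over time (assumption), the untreated share is g/(g + t). Stage 3 gives no value for g. The range 0 to 7 days is borrowed from the Stage 2 open trial, where questionnaires may be done up to a week ahead. The upper limit of t is 14 days.

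| g (days) | t = 14 | t = 7 |
|---|---|---|
| 0 | 0/14 = 0% | 0/7 = 0% |
| 1 | 1/15 = 7% | 1/8 = 12.5% |
| 3 | 3/17 = 18% | 3/10 = 30% |
| 7 | 7/21 = 33% | 7/14 = 50% |

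The day-14 column is the more plausible, since six bi-weekly surveys over 12 weeks fit a first survey near day 14.

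**4. Effect on a standardised difference.** For a score averaged per outing, with the SD unchanged (assumptions), the observed d is the true d × (1 − share). Take an illustrative true d of 0.5 and t = 14. If every woman had a 7-day gap, the observed value would be 0.5 × (1 − 0.333) = 0.33. For a 3-day gap it is 0.5 × (1 − 0.176) = 0.41, and for a 1-day gap 0.5 × (1 − 0.067) = 0.47. If only half the women had the 7-day gap, the average share is 0.5 × 33.3% = 16.7%, and d appears as 0.5 × (1 − 0.167) = 0.42.

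**5. Which outcomes are exposed?**
- Exposed: the two FAPB instruments, decisional balance scored per occasion, and drinking on occasions with the friend.
- Not exposed: the readiness ruler and alcohol knowledge, which are current-state measures, and the effect size from baseline to the last assessment.
- Only partly exposed: personalised alcohol strategies, since these are generated in the FMI.
- Sexual assault items: their stated recall is the preceding week. They reach before the session only if t < 7; at t = 3, for example, 4 of the 7 days precede it, whatever the baseline date. The planned analysis collapses them over the whole follow-up into one yes/no variable.

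**The case against.** The strongest reply is that the plan already intends baseline to be taken on the day. Stage 3 Procedures, the remuneration text and the SAP all point that way, and Section 9.1 puts consent at the session, so baseline could not come earlier. The permission in Section 10.3 is only a permission. The week's notice of the lab visit in Section 25.3 is offered as time to consider taking part, not as the date of the surveys.

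In addition, the End of Session Questionnaire, a post-intervention alcohol-awareness assessment, and the pre- and post-intervention data collection mentioned in Section 18.4 could each serve as the last assessment. Contamination would then be nil. The surveys are also labelled post-intervention. Finally, this is a pilot focused on feasibility and effect sizes, and the bias, where present, affects one wave and is conservative.

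Most of this stands as a limit on the point. A reader might infer that untreated outings will be scored as treated, or that a third to a half of the first window is untreated. The documents support neither: the first depends on both conditions above, and the second uses a gap taken from Stage 2. Nor do they support a claim that victimisation results are generally diluted.

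The objection does not remove the conflict. The permission in Section 10.3 is explicit and is backed by the online route in Section 25.2. The End of Session Questionnaire evaluates the session, not outings. No text excludes pre-FMI outings from the first survey.

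**Conclusion.** The point holds as a conditional one. Following the stated rules can place pre-FMI outings in the first follow-up, but only for women who complete baseline early and only if that baseline is the reference assessment. Its reach is limited to outing-linked measures at the first wave and the analyses that use that wave.

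For a score averaged per outing, the direction is toward no effect in the first-assessment model and the first-follow-up effect size, with later growth made to look steeper. The size cannot be derived from the documents. The illustrative shares of 0% to 33% at day 14 assume even spacing of outings and a gap of no more than 7 days. It is worth correcting because FAPB is a primary Aim 3 target and the correction is small.

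**What to change.** 1. **Section 10.3.** State that the first post-FMI survey, in both arms, covers only occasions after the FMI session, with the session date filled in automatically. State also that the one-week recall for the sexual assault items does not reach back past that date.
2. **Occasion record.** Add a date field for each reported outing.
3. **SAP.** Add one sentence excluding any occasion dated before the session from post-intervention outcomes.
4. **Consistency.** Reconcile the Section 10.3 permission and the online consent route in Section 25.2 with Stage 3 Procedures, its remuneration text, Sections 9.1 and 24.0, and the SAP's description of the baseline report.
5. **Optional.** Schedule the first survey near day 14.

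The cost is a survey instruction, a date field, one SAP sentence and some protocol editing. No extra participants or visits are needed. It should be done before Stage 3 data collection, because undated outings cannot be separated afterwards.

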#### **Friend-Based Assault Prevention Behavior Skills (FAPB)**

*Peer-Directed Bystander Behaviors for Sexual Assault Prevention (Baseline, bi-weekly).* We will use the 49-item Bystander Behaviors Scale for Friends (Banyard et al., 2014), which includes 4 subscales (1) the identification of sexual assault risk situations, (2) accessing resources, (3) planning ahead for risk situations, and (4) safety behaviors in risk settings. This measure will be adapted to include a broader

range of protective behaviors based on findings at Stage 1, and some of the items that refer to intimate partner violence will need to be reworded to assess sexual violence. Participants will complete this measure with respect to their target friend (i.e., did they do this for their friend) and also for themselves (i.e., did their friend do this for them?).

*Sexual Assault-Related Protective Behaviors (baseline, bi-weekly for all drinking occasions).* A measure developed by Armstrong et al., the Women's Peer-Directed Protective Strategy questionnaire (WPPS) will be used to evaluate assault-specific protective behaviors. This 24 item measure includes items such as, "I try to be aware and monitor where my friends are at all times," and, "I watch out for my friends in an attempt to keep them away from (risk) situations". Participants will complete this measure for their target friend (i.e., did they do this for their friend?) and also for themselves (i.e., did their friend do this for them?). Participants will be asked to rate frequency and how effective they perceived each behavior to be. They also will rate how they felt about it when they or their friend engaged in the behavior or did not engage in the behavior (when there was an opportunity) using a brief checklist of positive and negative feelings (e.g., good, relieved, safe, guilty, angry, scared). This will be based on information from qualitative participant interviews at earlier stages.

We also will assess whether the intervention resulted in unanticipated or adverse consequences, such as placing undue stress on a member of the dyad, or straining the friendship.

#### Readiness

*Readiness to Intervene (baseline, bi-weekly).* Participants will rate readiness for intervening on a 10-point likert-type scale, modeled after the Readiness Ruler (CEBP, 2010). This scale will be used in the FMI discussion, and also will be examined over follow-up (Moyers et al., 2009).

*Decisional Balance (baseline, bi-weekly).* The 10-item Decisional Balance Scale (Banyard et al., 2007) will be used to assess ambivalence about intervening in a potential assault situation. Responses regarding the decision about whether to intervene are rated along a 5-point Likert-type scale. Scores are computed for pros, cons, and negative consequences of intervention for each social occasion with the target friend.

#### Awareness and Strategies Regarding Alcohol Effects on Helping

Awareness of and strategies for alcohol's effects on helping behavior (baseline, post- and 12 weeks; strategies also assessed bi-weekly). We will assess participant understanding of the ways that alcohol may interfere with helping behavior. Questions will include levels at which alcohol is most likely to inhibit helping behavior (i.e., BACs of .08 or higher; Davis et al., 2009) and knowledge of alcohol's effects on risk recognition and responding. Based on focus group work (Stage 1) and collaborative discussions during the FMI, friends will generate a list of personalized strategies to be used to sustain helping motivation and behaviors during alcohol use, despite alcohol consumption (from Fillmore et al., 2000; Grattan & Vogel-Sprott. 2001). Strategies will include efforts such as sending pre-timed text reminders to check on friend, making plans for one member of the dyad to commit to moderate alcohol consumption, etc. In bi-weekly assessments, participants will be asked to what extent they engaged in these strategies during social occasions that involved alcohol.

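### Alcohol strategies are scheduled at baseline and in the untreated wait-list arm, but the only items described come from a list each dyad writes with the help of the FMI session

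*Combined protocol and SAP*

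**What the plan says.** **Content of the measure.** In section 10.3, under Awareness and Strategies Regarding Alcohol Effects on Helping, the strategies come from Stage 1 focus groups and from the session itself: "collaborative discussions during the FMI, friends will generate a list of personalized strategies". Two examples follow: pre-timed texts, and one friend committing to drink moderately. The use item is: "In bi-weekly assessments, participants will be asked to what extent they engaged in these strategies during social occasions that involved alcohol".

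**Schedule.** The same paragraph gives "baseline, post- and 12 weeks; strategies also assessed bi-weekly" for awareness and strategies together.

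**Order of events.** Section 4, Stage 3 Procedures, says of the FMI arm: "Each session will begin with a baseline assessment". Dyads in the "wait list control condition will be assessed once at baseline and again 12 weeks post-baseline", and they receive the FMI only after that. On content: "Assessment measures (baseline, 12 weeks) will mirror those administered to women in the FMI condition".

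**Use in the analysis.** The Statistical Analysis Plan (Outcome analyses) and section 16.1 (Aim 3) make an increase in alcohol knowledge and strategies part of goal 1. The variables compared between arms are "perceived barriers, readiness, alcohol knowledge and strategies, and implementation of FAPBs". Both texts then pool the arms, model change over 7 repeated measures, and compute standardized difference scores from baseline to the first and to the last follow-up.

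**The concern.** An outcome compared between arms, or from before to after, needs the same items on both sides of the comparison. Here the follow-up items are partly a product of the intervention, and nothing is described for a woman who has not yet had it. The items also differ from dyad to dyad, so equal scores in two dyads need not mean equal behavior.

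Reducing alcohol's interference with helping is one of the features the protocol presents as new. Section 16.2 says the main product of the trial is effect sizes to inform later studies, so an effect size that reflects a change of items rather than of behavior would carry forward into them. Stage 1 Procedures also acknowledges that women already make efforts of their own to help friends. Some of what is recorded after the FMI may therefore have been present before it, and the plan has no defined way to see that.

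**Working it through.** The question is what is measured and when, so the check is a count of assessments followed by a look at the effect-size formula.

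**Step 1: the plan's own count.** One pre-FMI record plus 12 weeks of bi-weekly surveys: 1 + 12/2 = 1 + 6 = 7. This reproduces the stated 7 repeated measures.

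**Step 2: where an FMI-written list can exist.**

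| Assessment | Strategies scheduled | List can exist |
|---|---|---|
| FMI arm, baseline | yes | no |
| FMI arm, six bi-weekly surveys | yes | yes |
| Wait-list arm, baseline | yes, mirrored | no |
| Wait-list arm, week 12, before its FMI | yes, mirrored | no |
| Wait-list arm, six surveys after its own FMI | yes | yes |

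The FMI arm has 6 of 7 and the untreated wait-list arm 0 of 2. In the pooled change models, the pre-FMI record has no list in any of the 24 + 24 = 48 dyads.

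**Step 3: effect on the difference score.** Let Y0 be the pre-FMI score, and Y1 and Y6 the first and last follow-up scores. The plan's effect sizes are mean(Y1 − Y0)/SD(Y1 − Y0) and mean(Y6 − Y0)/SD(Y6 − Y0). The documents do not define Y0. The possibilities are:

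- Y0 left blank: no difference can be formed.
- Y0 set to zero: the first ratio becomes mean(Y1)/SD(Y1). That is a level of use, not a change, and it credits any existing use to the FMI.
- Y0 from generic items G, and Y1 from dyad k's list L(k): Y1 − Y0 = [use of L(k) after − use of L(k) before] + [use of L(k) before − use of G before]. Only the first bracket is change in behavior. The second reflects the switch of items, is not observed, and can have either sign.

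**Step 4: effect on the between-arm contrast.** At week 12 the FMI arm would be scored on L(k) and the wait-list arm on G or on nothing. The arm difference then contains the same item-set term.

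**Step 5: the knowledge half.** Knowledge is scheduled at baseline, post and 12 weeks, which is 3 occasions, and its questions do not depend on a list. The SAP nevertheless groups it with strategies in models described with 6 and 7 repeated measures. Section 16.1 ties the 7 records to protective behavioral strategies, while the SAP widens them to all variables of interest. This is a wording mismatch, separate from the list problem.

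**The case against.** The strongest reply is that the measure is under-described, not impossible. A strategies assessment is scheduled at baseline and mirrored in the wait-list arm, and the word *also* in the schedule leaves room for a general measure alongside the bi-weekly use item. The Background (The proposed Intervention) says strategies will be explored in Stage 1, and any woman could rate the examples in section 10.3, so a common pool could exist before the first Stage 3 dyad is seen. Section 25.2 refers to a measures table that is not in the text available for review. The trial is a pilot, and readiness and FAPB have named instruments and are unaffected.

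Much of this stands. A reader might infer that no strategies measure exists at any baseline and that goal 1 cannot be answered. The documents do not support that, because the assessment is planned and usable source material is due from Stage 1.

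It does not remove the problem. No text available says that a common pool will be the instrument, and none gives items or scoring for untreated women. Even a general baseline measure would leave follow-up resting on the dyad's own list, which is the third case in step 3. Nor do the neighboring scales fill the gap: the PBSS is included because women may limit drinking, and the WPPS and the bystander scale measure FAPB, which the SAP lists separately from alcohol strategies.

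**Conclusion.** The point holds in a bounded form. As written, the strategies part of the between-arm contrast and of the baseline-to-follow-up difference scores is not interpretable, because untreated women have no defined items and follow-up scores use items that differ between dyads and match no pre-FMI measure. Alcohol knowledge is not affected by the list problem.

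The size is best given as the count: 6 of 7 in the FMI arm and 0 of 2 in the untreated wait-list arm. A reader might go further and infer an inflated effect of some stated size. The documents do not support a figure. They never propose scoring untreated women as zero, and they give no scale, mean or SD for this measure.

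The conclusion assumes that the bi-weekly use item refers to the personalized list, which is the plain reading of the paragraph, and that the unseen measures table does not define a common item set. If it does, and that set is also the follow-up outcome, only the text of section 10.3 and the SAP needs correcting.

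**What to change.** Before the first Stage 3 baseline is collected:

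- Build one fixed checklist of alcohol-helping strategies from the Stage 1 material. Give the same items to all women in both arms at baseline, at wait-list week 12 and at every bi-weekly survey. State the scoring in section 10.3 and name this score in the SAP as the alcohol-strategies outcome.
- Report use of the dyad's own list only as FMI adherence, outside the between-arm and pre-post effect sizes.
- Model alcohol knowledge only at baseline, post and 12 weeks, and say so where the SAP describes 6 and 7 repeated measures.

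Comparable items would then be available at 7 of 7 and 2 of 2 assessments, giving a pre-FMI baseline and a week-12 comparison between arms. The cost is a few survey items, some SAP wording and a less personalized outcome. The timing matters because a baseline not collected before the FMI cannot be recovered.

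This does not supply a concurrent wait-list value at the first post-intervention assessment, since that arm has no bi-weekly survey before its own FMI. That is a separate issue affecting all outcomes.
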